8 STUDY OBJECTIVES

8.1 Primary Objectives

- To determine whether E2027 is superior to placebo on the cognitive endpoint of MoCA in subjects with DLB after 12 weeks of treatment
- To determine whether E2027 is superior to placebo on the global clinical endpoint of CIBIC-Plus after 12 weeks of treatment

8.2 Secondary Objectives

(Order of secondary objectives revised per Amendment 05)

- To determine whether E2027 is superior to placebo on the following secondary endpoints after 12 weeks of treatment:
 - Clinician Global Impression of Change in Dementia with Lewy Bodies (CGIC-DLB)
 - Cognitive Fluctuation Inventory (CFI)
 - Mini-Mental State Examination (MMSE)
 - Neuropsychiatric Inventory (NPI)
- To evaluate the safety and tolerability of E2027 in subjects with DLB
- To characterize the population pharmacokinetics (PPK) of E2027 in subjects with DLB, including evaluation of the effects of intrinsic and extrinsic factors on E2027 PK

8.3 Exploratory Objectives

- To explore the efficacy of E2027 compared to placebo on the following endpoints after 12 weeks of treatment:
 - Scales for Outcome in Parkinson's disease-Sleep (SCOPA-Sleep)
 - Dementia-related quality of life as assessed by the Dementia Quality of Life Measure (DEMQOL; interview of subject) and Dementia Quality of Life Measure by Proxy (DEMQOL-Proxy; interview of caregiver or informant about subject)
 - General health status as assessed by the EuroQol- 5 Dimension questionnaire (EQ-5D; completed by subject) and EuroQol- 5 Dimensions questionnaire by Proxy Version 1 (EQ-5D Proxy; caregiver or informant completion of report about subject)
- To evaluate the relationship between PK exposure of E2027 and its effects on various efficacy and safety endpoints
- To explore the PK/PD relationship between the exposure of E2027 in CSF/plasma and its effects on CSF PD biomarker endpoints, including CSF cGMP, if data permit
- To explore the relationship between the E2027 PD effects (including CSF cGMP) with E2027 effects on various efficacy endpoints, if data permit
- To explore collected pharmacogenomic (PGx) samples by investigating heterogeneity in clinical features of disease, including differences in baseline characteristics as well as response to compound (efficacy, safety and/or absorption, distribution, metabolism, and excretion [ADME]). These exploratory analyses are not limited to this protocol or project. These findings may be used for identification and validation of new drug targets.

9 INVESTIGATIONAL PLAN

9.1 Overall Study Design and Plan

This is a multicentre, randomized, double-blind, placebo-controlled, parallel-group study in subjects with dementia with Lewy bodies (DLB) who will be treated with placebo or a dose of E2027 (50 mg QD) for 12 weeks. An overview of the study design is presented in [Figure 1](#).

In some of the countries selected for this study, donepezil is approved for DLB, with AChEI and increasingly memantine often used as part of standard care in patients with DLB. Therefore, the study design allows for add-on therapy to standard of care for DLB, which includes AChEI and/or memantine at stable doses, except for any prohibited medications specified in this protocol. Subjects who are not receiving AChEI and/or memantine are also eligible, but are not permitted to start such medications during the study. (revised per Amendment 03) Randomization will be stratified based on whether subjects are on a stabilized dose of AChEI or not and by geographical region (ie, North America, Europe, Japan). Up to approximately 20% of randomized subjects will be on memantine. (revised per Amendment 04) Subjects will be randomized to placebo and a dose of E2027 (50 mg QD) in a ratio of 1:1.

For all subjects study participation will comprise 2 phases: Prerandomization and Randomization. The Prerandomization Phase will last for up to 6 weeks and will include a Screening Period (up to 5 weeks) and a Baseline Period (1 week). The Randomization Phase will last for 16 weeks and will include a Treatment Period (12 weeks) and a Follow-up Period (4 weeks).

[figure not shown]

Figure 1 Study Design for Study E2027-G000-201

*Subjects will have follow-up 4 weeks after the end of the treatment and a final assessment completed.

R = randomization

9.1.1 Screening Period

Screening will occur between Day -42 and Day -8. The purpose of the Screening Period is to obtain informed consent and to establish protocol eligibility. Informed consent will be obtained after the study has been fully explained to each subject and before the conduct of any

screening procedures or assessments. All subjects will be assessed for eligibility through review of medical history, physical examination (including neurological examination), laboratory tests, vital signs and electrocardiograms (ECGs). They will be assessed on clinical scales of cognition and depression, safety magnetic resonance imaging (MRI of the brain) and dopamine transporter (DAT) brain imaging or myocardial scintigraphy ($[^{123}\text{I}]$ meta-iodobenzylguanidine [MIBG]) (if indicated in individual subjects and not previously performed) to confirm that they meet the diagnostic criteria and severity for DLB. Their motor features will be assessed on the Movement Disorders Society (MDS) Unified Parkinson's Disease Rating Scale Part III: Motor Examination (UPDRS-III) and staged by the Hoehn and Yahr Scale (HYS). Their history of suicidality will be assessed by the Columbia Suicide Severity Rating Scale (C-SSRS). They will also be assessed regarding other medical conditions and concomitant medications to ensure that these are stable with no changes to treatment required and that they do not interfere with their safety or study procedures.

Eligibility assessments at Screening will be conducted in tiers and subjects will need to satisfy eligibility criteria in each tier before proceeding to the next tier. In Tier 1 demographics, medical history (including history of DLB and other medical conditions) and concomitant medications will be reviewed. In Tier 2, clinical assessments on cognition and depression will be conducted in the morning (whenever possible) in subjects in the following order: MMSE and Geriatric Depression Scale (GDS) should be done first, followed by the MoCA and SCOPA-Sleep. The caregivers or informants will also complete the Short Fluctuation Questionnaire (SFQ), CFI and the NPI. If the eligibility criteria regarding the MMSE and GDS are not met, the other procedures (MoCA, SCOPA-Sleep, SFQ, CFI and NPI) do not have to be performed and the subject should be screen failed. In Tier 3 subjects will be assessed with the Modified Hachinski Ischemic Scale, UPDRS-III, HYS and C-SSRS. In Tier 4 subjects will undertake physical examination, vital signs, ECG and clinical laboratory tests. In Tier 5, subjects will be assessed by safety MRI for brain abnormalities that may affect eligibility. In Tier 6, if indicated as judged by the investigator, individual subjects may also undertake DAT brain imaging scan or myocardial MIBG scan to help establish their diagnosis. It is recommended that where appropriate Tiers 1 to 4 should be performed on the same day and Tiers 5 and 6 on a separate day. However, the investigator may perform the various tiers on separate days as appropriate for each subject. The scores of various clinical scales (including NPI, SFQ, and UPDRS-III) and cognitive tests (MMSE, MoCA) at Screening will be reviewed by a central process. Subjects who are diagnosed by the investigator with DLB but whose scores on clinical scales or cognitive tests are found not to be consistent with the diagnosis during central review will be discussed with the investigator to determine their eligibility.

Due to the intrinsic variability of cognitive functions in DLB, subjects who screen fail at Tier 2 may be rescreened after at least 30 days, but as a guide, rescreening frequency should not be more frequent than once every 4 months and a subject should not be rescreened more than 2 times under the same version of the eligibility criteria. Subjects who are deemed eligible after passing all tiers at Screening will proceed to the Baseline Visit.

9.1.2 Baseline Period

The Baseline Visit may take place at any time up to 7 days before the first dose of study drug (Day 1, ie, during Day -7 to Day -1, but should take place at least 2 weeks after the Screening Visit Tier 2 assessments). In subjects who had DAT brain imaging scan or MIBG scan during Screening, the Baseline Visit must take place at least 1 week after the scan. Study assessments should be conducted in the morning (whenever possible). Cognition will be assessed by the MoCA, which should be the first clinical scale to be administered before any invasive procedures. It is recommended that after the MoCA the following efficacy assessments in subjects should be performed in the following overall order (other study assessments may be conducted in between these efficacy assessments): Clinician Interview Based Impression of Severity plus Caregiver Input (CIBIS-Plus) and SCOPA-Sleep. The subject will be interviewed to complete the DEMQOL. The EQ-5D will be self-administered and completed by the subject. The caregiver or informant will also complete the CIBIS-Plus, NPI, CFI, EQ-5D Proxy Version 1 and will be interviewed to complete the DEMQOL-Proxy. The rater administering the CIBIS-Plus should be independent of the rater(s) who administer the other clinical scales.

At Baseline Visit subjects will be assessed regarding other medical conditions and concomitant medications (including medications for DLB) to ensure that these remain stable with no changes to treatment required and that they do not interfere with their safety or study procedures. Other safety assessment including vital signs, ECGs, laboratory tests and C-SSRS will also be conducted. The results of clinical laboratory tests at the Baseline Visit must be reviewed by the investigator in accordance with Exclusion Criterion 17 before proceeding to randomization, unless these tests showed no clinically significant out of range values at Screening.

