9.1.3 Randomization Phase/Treatment Period

After completing study assessments at the Baseline Visit, subjects who continue to be eligible will proceed to the Randomization Phase, and will be randomized to placebo or E2027 (50 mg QD). They will be provided with study drug (placebo or E2027) to start administration in the morning of Day 1 at home. They will continue to take study drug for 12 weeks. During the Treatment Period study visits will be conducted after 2, 4, 6, 9 and 12 weeks on study drug. Safety assessments will be conducted at all these visits. Efficacy assessments will be performed after 6 and 12 weeks on study drug and should be performed at approximately the same time of the day as at the Baseline Visit whenever possible (preferably in the morning). The MoCA should be the first clinical scale to be administered before any invasive procedures. As far as is possible a subject should have the same rater administering the MoCA throughout his/her participation in the study. It is recommended that other efficacy assessments in subjects should be performed in the following overall order (other study assessments may be conducted in between these efficacy assessments): CIBIC-Plus, MMSE (after 12 weeks only) and SCOPA-Sleep. As far as is possible a subject should have the same rater administering the CIBIS/C-Plus throughout his/her participation in the study. The rater administering the CIBIC-Plus should be independent of the rater(s) who administer the other clinical scales. The subject will self-complete the EQ-5D. The caregiver or informant will also complete the CIBIC-Plus,

NPI, CFI, and EQ-5D Proxy Version 1. In addition at the study visit after 12 weeks on study drug interviews with the subject and the caregiver or informant will be conducted to complete the DEMQOL (subject) and DEMQOL-Proxy (caregiver or informant). Safety assessments will be conducted at these visits, including review of adverse events (AEs), vital signs, ECG, laboratory safety tests, C-SSRS and UPDRS-III. The investigator will review all the efficacy endpoints and safety data at the visits after 6 weeks and 12 weeks on study drug and formulate the CGIC-DLB of the subject's clinical status from Baseline.

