al., 2015). The use of MMSE as a secondary efficacy endpoint on cognition allows benchmarking of the efficacy of E2027 with other precognitive drugs in these indications. The CFI evaluates within subject fluctuation of cognitive symptoms and it showed treatment benefit with donepezil in subjects with DLB (Mori, et al, 2012).

The NPI evaluates behavioral and psychiatric features in subjects with dementia and it showed benefit in subjects treated with rivastigmine in PDD (Burn, et al., 2006) and in subjects treated with donepezil in DLB (McKeith, et al., 2000; Mori, et al., 2012). It is therefore used as one of the secondary efficacy endpoints in Study 201 to evaluate efficacy on non-cognitive features.

Sleep disturbance is common in PDD and DLB (Boddy et al, 2007). The effects of E2027 on sleep in animal models were not specifically evaluated. In Study 201 the effects of E2027 on sleep will be evaluated with the Scales for Outcome in Parkinson's disease—Sleep (SCOPA-Sleep) which will be an exploratory efficacy endpoint. This scale showed improvement in sleep quality in subjects with Parkinson's disease psychosis who were treated with pimavanserin (Cummings, et al., 2014).

The CGIC-DLB provides an overall clinician-determined summary measure of change from the subject's clinical status at Baseline Visit that takes into account all available information from the efficacy endpoints above (which include cognitive function, non-cognitive symptoms, behaviour and the impact of the symptoms on the patient's ability to function) and safety data. The CGIC-DLB is scored by the investigator and is separate from the evaluation with the CIBIC-Plus by an independent rater. A similar CGIC endpoint was used in a previous study in subjects with AD (Grove, et al., 2014).

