#### 5.4.2 Secondary Efficacy Analyses

Table 5 Secondary Efficacy Analyses			
Score		Analysis for non-EMA Registration	Analysis for EMA Registration
CGIC-DLB	Secondary analysis	GLMM	Proportional odds model with control-based pattern imputation
	Additional secondary analysis	Proportional odds model with control-based pattern imputation	GLMM
CFI	Secondary analysis	MMRM	Control based mean imputation with Mehrotra
	Additional secondary analysis	Control based mean imputation with Mehrotra	MMRM

MMSE	Secondary analysis	ANCOVA and multiple imputation (MI) assuming MAR	ANCOVA and control-based pattern imputation
NPI	Secondary analysis	MMRM	Control based mean imputation with Mehrotra
	Additional secondary analysis	Control based mean imputation with Mehrotra	MMRM
MoCA	Additional secondary analysis	Control based mean imputation with Mehrotra	MMRM
CIBIC-Plus	Additional secondary analysis	Proportional odds model with control-based pattern imputation	GLMM

Table 5 details the analyses for the secondary endpoints. Further details are described below.

The CGIC-DLB scale will be analyzed as ordinal response data in a manner similar to the primary analysis of co-primary endpoint based on CIBIC-Plus, according to both methods for non-EMA and EMA registrations.

CFI is a continuous variable and will be analyzed in a manner similar to the primary analysis of co-primary endpoint based on MoCA, according to both methods for non-EMA and EMA registrations.

For the non-EMA registration, MMSE will be analyzed using ANCOVA with MI assuming MAR. For the EMA registration, MMSE will be analyzed using ANCOVA with control-based pattern imputation at subject level for missing data handling (Yang Yuan, Paper SAS270-2014, SAS Institute Inc.). The ANCOVA model will include corresponding baseline as a covariate, with treatment group and randomization stratification variables as factors.

NPI will be analyzed in a manner similar to the primary analysis of co-primary endpoint based on MoCA, according to both methods for EMA, and non-EMA registrations.

The details of calculating all efficacy endpoints are presented in Section 8.3 ALGORITHMS FOR EFFICACY PARAMETERS.

Additional secondary efficacy analyses will be performed with or without inclusion of efficacy data collected after treatment discontinuation:

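### Efficiency point on one secondary endpoint: the MMSE ANCOVA adjusts only for the Screening eligibility MMSE, although a later pre-treatment MoCA is already collected and could be added as a covariate

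*Protocol*

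**What the plan says.** - **When MMSE is taken.** In Tier 2 of Screening (Protocol 9.1.1), "MMSE and Geriatric Depression Scale (GDS) should be done first, followed by the MoCA and SCOPA-Sleep". Inclusion Criterion 3 uses this score, with limits of 14 and 26. In the Treatment Period the assessment order (Protocol 9.1.3) is "CIBIC-Plus, MMSE (after 12 weeks only) and SCOPA-Sleep". Table 6 shows no MMSE at the Baseline Visit or at Week 6. MoCA is done at Screening, Baseline, Week 6 and Week 12.
- **Timing.** For Screening, "Screening will occur between Day -42 and Day -8". For Baseline, "The Baseline Visit may take place at any time up to 7 days before the first dose of study drug", and that visit "should take place at least 2 weeks after the Screening Visit Tier 2 assessments".
- **Rescreening.** Because cognition varies in DLB, "subjects who screen fail at Tier 2 may be rescreened after at least 30 days", with a limit of two rescreens under one version of the criteria.
- **Definition of baseline.** SAP 8.1.1 takes the most recent value before treatment. For MMSE, that is the Screening score.
- **MMSE model.** For both registrations, SAP 5.4.2 states: "The ANCOVA model will include corresponding baseline as a covariate, with treatment group and randomization stratification variables as factors". The missing-data method is multiple imputation under MAR (non-EMA) or control-based pattern imputation (EMA). The variables in these imputation models are not listed.
- **Role of MMSE.** It is third among the efficacy secondaries. Protocol 9.2 says: "The use of MMSE as a secondary efficacy endpoint on cognition allows benchmarking of the efficacy of E2027".

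**The concern.** MMSE is in a weaker position than the other cognitive measures. MoCA, CFI and NPI have a Baseline Visit value and a Week 6 value that enters a repeated-measures model. MMSE has one planned pre-treatment value and one planned on-treatment value, so baseline covariates are its main source of precision. The single covariate it does have is the score that admitted the subject, so its range is restricted. It was taken at least two weeks before a visit at which another cognitive test was given.

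The protocol already accepts adjustment across scales. Section 9.7.1.6.1 proposes to examine baseline MMSE as an additional covariate in the primary model. The converse, baseline MoCA in the MMSE model, appears nowhere. What is at stake is the width of the MMSE confidence interval and the power of that comparison, not their validity.

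**Working it through.** **The plan's own figures.** The documents give no SD, power or sample size for MMSE, so there is no MMSE figure to reproduce. The overall size does reproduce: 80 completers per arm with 12% dropout gives 80 / 0.88 = 90.9, so 91 per arm and 182 in total. The 80 completers per arm are the base below.

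**Lag (no Day 0).**
- Baseline Visit on Day -1: Tier 2 no later than Day -1 - 14 = Day -15, which is 15 days before first dose.
- Baseline Visit on Day -7: Tier 2 no later than Day -21.
- Start of the Screening window: Day -42.
- Distance to a Day 84 outcome: 84 + 15 - 1 = 98 to 84 + 42 - 1 = 125 days for Screening MMSE, against 84 to 90 days for a Baseline Visit MoCA.

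**Gain from one more covariate.** Let r be the partial correlation of baseline MoCA with Week 12 MMSE, given Screening MMSE. Then:

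- residual variance ratio = 1 - r²
- standard error ratio = √(1 - r²)
- effective completers per arm = 80 / (1 - r²)
- power, if the planned ANCOVA had 80% = Φ[(1.960 + 0.842) / √(1 - r²) - 1.960]

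| r (assumed) | Variance | Standard error | 80 per arm acts like | Power |
|---|---|---|---|---|
| 0 | 0% | 0% | 80 | 80.0% |
| 0.1 | -1% | -0.5% | 80.8 | 80.4% |
| 0.2 | -4% | -2.0% | 83.3 | 81.6% |
| 0.3 | -9% | -4.6% | 87.9 | 83.6% |
| 0.4 | -16% | -8.3% | 95.2 | 86.4% |

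**The same in ordinary correlations.** Let r1 be Screening MMSE with Week 12 MMSE, r2 baseline MoCA with Week 12 MMSE, and r12 the two covariates with each other. Then R² = (r1² + r2² - 2·r1·r2·r12) / (1 - r12²), and the variance ratio is (1 - R²) / (1 - r1²). Illustrative assumed sets:

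- (0.6, 0.6, 0.6): R² = 0.288 / 0.64 = 0.45; ratio 0.55 / 0.64 = 0.859, a 14% cut.
- (0.7, 0.6, 0.7): R² = 0.262 / 0.51 = 0.514; ratio 0.953, a 5% cut.
- (0.7, 0.5, 0.7): R² = 0.25 / 0.51 = 0.490; ratio 1.00, no cut.

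**Price of the extra term.** With 160 completers and main effects for treatment, baseline MMSE, AChEI use and three regions, the planned model has 6 parameters and 160 - 6 = 154 residual degrees of freedom. One more term leaves 153. If the covariate were useless, the variance would rise by roughly 1/153, or 0.7%. Break-even is thus at a partial correlation of about 0.08 (0.08² = 0.0064).

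**The case against.** The strongest reply is that nothing is wrong. Adjusting for an endpoint's own baseline and the stratification factors is the SAP's general rule (5.3.2), and under randomization it is valid. The two-week gap is a scheduling rule, and the benefit is assumed, since no MMSE correlation is given. All of this stands, and it is why the point is optional.

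Several stronger readings are tempting, and the documents do not support them:

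- **That an old, range-restricted baseline biases the MMSE result.** The entry limits and any regression to the mean apply equally to both randomized arms.
- **That the gain is large.** A cut of 36% follows from correlations (0.5, 0.7, 0.5), but MoCA would then predict Week 12 MMSE better than MMSE predicts itself. Where MMSE is the better predictor, cuts are mostly small.
- **That every FAS subject has a Baseline Visit MoCA.** The FAS asks for a baseline value. Under SAP 8.1.2 that is the last non-missing pre-treatment value, which may come from Screening, and SAP 8.3 sets the MoCA total to missing if any component is missing.
- **That MoCA is free of selection, or measures the same thing.** Selecting on a correlated MMSE restricts MoCA indirectly. Protocol 9.2 says MoCA puts more weight on executive, attention and visuospatial function.
- **That the MMSE is badly out of date.** The lag that matters for the covariate is to Week 12, 98 to 125 days against 84 to 90. Longer lags need the exceptional extensions in the Table 6 footnotes. One MoCA also carries visit-to-visit fluctuation.

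The 15-day minimum is itself worded as an expectation, and an unscheduled pre-dose MMSE would count as baseline, although none is planned.

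**Conclusion.** The facts hold. The planned baseline MMSE is the Screening eligibility score, normally from Day -15 or earlier, and the MMSE ANCOVA contains no other cognitive score. The planned analysis is valid. The omission can only cost precision, and only on this one secondary endpoint.

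The size rests on a partial correlation that the documents do not report. Over 0.1 to 0.4 the variance reduction is 1% to 16%. It may be near zero, and a useless covariate would cost under 1%. The power figures also assume that the planned MMSE comparison would have 80% power, which the documents neither state nor imply. This is a free improvement of optional priority.

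**What to change.** Before unblinding, amend SAP 5.4.2 as follows:

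1. Add the analysis-baseline MoCA total score as a second continuous covariate in the MMSE ANCOVA for both registrations. Define it as the last non-missing pre-treatment value, normally from the Baseline Visit and otherwise from Screening. With this fallback, missing covariate values should be rare.
2. Include the same score in the matching MMSE imputation models, so that the imputation and analysis models agree. Those models' variables are not listed now, so this is also the place to list them.
3. Keep Screening MMSE as the baseline for the change score and as the first covariate.

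The cost is 1 degree of freedom and a small SAP edit covering two ANCOVAs and their imputation models. No new data are needed. The term should be fixed in advance, because adding it after unblinding would look selective. If the sponsor wants to know the likely gain first, the partial correlation can be estimated from pooled blinded data, which it has already used for the MoCA SD (SAP 4).
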